Endpoints:	
Primary endpoint: Equivalence between the detection of parameters useful for the diagnosis of OSA using the SOUNDI system and standard polysomnographic methods.
 
Secondary endpoints:
 
 • evaluation of satisfaction with the use of SOUND I after the night of recording the parameters, by completing a questionnaire. • safety and tolerability of the SOUNDI device using it recording of adverse events.
Estimated enrollment:	50 subjects
Study population:	Adult subjects belonging to the clinical centre, to carry out a polysomnography for suspicion of a breathing disorder sleep.
Inclusion criteria and exclusion:	
Inclusion criteria:
 
 • Signature of informed consent • Patients of both sexes, of any ethnicity • Age between 20 and 70 years • Prescription, from clinical practice, to carry out a polysomnography on suspicion of a breathing disorder in sleep. 
Exclusion criteria:
 
 • Women during pregnancy • Insufficient cooperation/degree of collaboration in following the procedures required by the study • Participation in another clinical study. • Allergy to one of the materials in the device • Pacemaker users.
Procedures:	
Some data will be collected during a visit anthropometric devices will be positioned simultaneously for polysomnography:
 
 - a traditional polysomnigraph, as prescribed - the experimental Soundi device. 
During the night, at the patient's home, the following parameters will be acquired for at least 8 consecutive hours: oro-nasal flow, thoracic and abdominal respirogram, snoring, ECG, arterial oxygen saturation, body position.
 
The following morning the subject will return to the clinics to return the two systems and complete a simple satisfaction questionnaire prepared for the study.

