	
Efficacy analyzes will be carried out on all patients who have completed the evaluation and whose data will be considered evaluable.
 
For each parameter, the agreement between the measurement carried out with the SOUNDI method and the one carried out with polysomnography will be evaluated using the Bland-Altman graph and the Concordance Correlation Coefficient (CCC).
 
Statistical considerations:
 
Descriptive statistics will be used to evaluate the subject's satisfaction with using SOUNDI.
 
The safety analyzes will be carried out on all patients to whom the Sound device and the polysomnography device have been applied, regardless of the validity of the data collected. The safety analyzes will be of a descriptive nature.
 
A sample of 50 analyzable patients will guarantee a power of 90% in determining six values of the parameters detected with the SOUNDI method which are in agreement with those measured by polysomnography.

Study duration:
	
The expected duration of enrollment of all subjects is approximately 6 months.
 
The expected duration of the study for the subject is a maximum of 24 hours.
 
The overall duration of the study will be 1 year.

Summary

1. Abbreviations	9
2. Operational Background	10
2.1 Rational	10
2.2 Background	10
3. Information on the medical device Pre-clinical	11
3.1 trials Trials on healthy	14
3.2 volunteers Risks and	14
3.3 benefits	15
4. Study Design Comparison	15
4.1	15
5. Objectives of the study	16
5.1 Primary objective	16
5.2 Secondary objectives	16
6. Study population Number of	16
6.1 patients Inclusion	16
6.2 criteria Exclusion	16
6.3 criteria	16
7. Study procedures	16
7.1 Compliance with Followup	17
7.2 procedures	17
8. Duration of the study	18
8.1 Interruption and withdrawal of subjects from the clinical investigation	18
8.2 Early closure or suspension of the study	18
9. Evaluation of effectiveness	19
9.1 Primary endpoint	19
9.2 Secondary endpoint	19
10. Evaluation of the safety and vigilance of the medical device	19
10.1 Recording of adverse events Definitions	19
10.2 Classification	19
10.3 of adverse events Predictable/expected	20
10.4 adverse events and effects Reporting of adverse	22
10.5 events Notification to the Competent	22
10.6 Authorities 10.7 Consequences on risk	22
analysis	23
11. Statistics	23
11.1 Effectiveness analysis	23
11.2 Securityanalysis	23
11.3 Analysis set	24
11.4 Systematic errors - bias	24
12. Medical device	24

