9.1 Primary endpoint

The primary endpoint of the study is the equivalence between the detection of parameters useful for the diagnosis of OSA using the SOUNDIV system and standard polysomnographic methods.

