11.1 Effectiveness analysis

The continuous variables will be reported as the mean value and standard deviation or as the median and interquartile range in the case of non-normally distributed data. Therefore, for each parameter the agreement between the measurement carried out with the SOUNDI method and the one carried out with polysomnography (gold standard) will be evaluated using the Bland-Altman graph and the Concordance Correlation Coefficient (CCC) [6]. In short, this graph represents the value of the differences of the measurements carried out with two methods differ from their average[7]. The CCC varies between -1 and 1, values between 0.61 and 0.80 indicate substantial agreement while values greater than 0.81 almost perfect agreement according to the Landis and Koch scale [8].

Descriptive statistics will be used to evaluate the subject's satisfaction with using SOUNDI.

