11.2 Securityanalysis

The safety analyzes will be carried out on all patients to whom the Sound device and the polysomnography device have been applied, regardless of the validity of the data collected.

In general, safety analyzes will be descriptive in nature. The frequency, severity, severity and causal relationship of adverse events will be tabulated.

Both the number and percentage of events and patients experiencing an event will be presented. Additionally, adverse events that led to study suspension and device defects reported.

Sample size.

A sample of 50 analyzable patients will guarantee a power of 90% in determining six values of the parameters detected with the SOUND I method are in agreement with those measured by polysomnography. The estimate was made considering: i) a z-head and a tail with a significance level of 5%; ii) a value of the CCCparia 0.60 below H0; iii) a value of the CCCparia 0.81 below H1 . Sample sizing was performed using PASS2021(PowerAnalysisandSampleSizeSoftware(2021).NCSS,LLC.Kaysville,Utah,USA).

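### The primary endpoint is called equivalence with no acceptable difference stated, while the only powered test can show no more than a concordance correlation above 0.60

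*Protocol*

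**What the plan says.** **Endpoint.** Protocol section 9.1 begins: "The primary endpoint of the study is the equivalence between the detection of parameters useful for the diagnosis of OSA". The endpoints row of the synopsis says the same: "Equivalence between the detection of parameters useful for the diagnosis of OSA using the SOUNDI system and standard polysomnographic methods". Neither place gives a margin, an acceptable difference or a primary index.

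**Sample size.** The paragraph at the end of section 11.2 asks for 50 analysable patients and 90% power. Its inputs are "i) a z-head and a tail with a significance level of 5" percent (a garbled phrase, read here as a one-tailed z-test) and "ii) a value of the CCCparia 0.60 below H0; iii) a value of the CCCparia 0.81 below H1". The statistical considerations in the synopsis describe what is powered as "values of the parameters detected with the SOUNDI method which are in agreement with those measured by polysomnography", which is agreement, not equivalence.

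**Analysis.** Section 11.1 plans two methods for each parameter, the Bland-Altman graph and the CCC. It sets no limits for the Bland-Altman differences. For the CCC it gives the Landis-Koch reading: "values between 0.61 and 0.80 indicate substantial agreement while values greater than 0.81 almost perfect agreement". It does not describe these bands as a criterion for success.

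**The concern.** An equivalence claim needs a statement, fixed in advance, of how large a difference is still acceptable, and a test that excludes larger ones. The protocol has no such statement. Its one hypothesis concerns a different quantity and a modest threshold, so a study that passes its own test would still not have shown what the primary endpoint names. The value 0.81 does not close the gap: it is the true CCC assumed for the power calculation, not a value that a significant result establishes.

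The study is a pre-marketing validation against the reference method, so the wording of the primary endpoint is the claim that will be carried forward. As written, the plan would let a result that excludes only CCC values up to 0.60 be reported as equivalence with polysomnography.

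**Working it through.** **Inputs** (protocol, sample-size paragraph in 11.2): CCC 0.60 under H0, CCC 0.81 under H1, 5% one-tailed (z = 1.645), power 90% (z = 1.282), n = 50.

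**Method.** Fisher z-transform of the CCC, with standard error 1/√(n−3) and, as a check, 1/√(n−2). This assumes no location or scale shift between the devices; the protocol gives no distributions.

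**1. The plan's own figure.**
- atanh(0.81) − atanh(0.60) = 1.1270 − 0.6931 = 0.4339
- n = (1.645 + 1.282)² / 0.4339² + 3 = 45.5 + 3 = 48.5, so 49 (48 with the n−2 form)
- Power at n = 50 is 0.908 (n−3) or 0.913 (n−2)
- A two-sided 5% test would need 58 or 59, which supports the one-tailed reading

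The stated 50 is therefore reproduced to within two patients.

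**2. What passing the test requires.** The smallest observed CCC that rejects 0.60 at n = 50 is tanh(0.6931 + 1.645/√47) = tanh(0.933) = 0.732 (0.731 with n−2). A device with a true CCC of 0.70 passes in about 33% of trials, and one with 0.75 in about 61%.

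**3. What that means on the scale of differences.** Assume equal SDs and no bias. The SD of the differences is then SD × √(2(1 − CCC)), and the 95% limits of agreement are ±1.96 times that:

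| CCC | 95% limits, in between-patient SDs |
|---|---|
| 0.60 | ±1.75 |
| 0.73 | ±1.44 |
| 0.81 | ±1.21 |

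Excluding a CCC of 0.60 thus leaves room for device differences larger than one between-patient SD.

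**4. Secondary point: the bands without a confidence limit.** The one-sided 95% lower limit is tanh(atanh(observed) − 1.645/√47):

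| Observed CCC | Label in 11.1 | Lower limit |
|---|---|---|
| 0.61 | substantial | 0.44 |
| 0.65 | substantial | 0.49 |
| 0.70 | substantial | 0.56 |
| 0.73 | substantial | just under 0.60 |

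From 0.61 to about 0.73 the label is favourable although 0.60 is not excluded. The chance of landing in that zone is about 9% at the planned true CCC of 0.81, 35–36% at 0.75 and 53–54% at 0.70.

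**5. One index or several.** Section 7 lists about eleven indices: four forms of AHI, ODI, three saturation measures, two heart-rate measures and body position. Power of about 0.91 applies to one. If all had to pass and were independent (an assumption), joint power would be 0.908² to 0.913², about 0.82–0.83, for two, and 0.908¹¹ to 0.913¹¹, about 0.35–0.37, for eleven. Positive correlation would raise these towards 0.91.

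**The case against.** The text reads like a machine translation, so *equivalence* may be loose wording for agreement. The synopsis statistics, 11.1 and the sample-size paragraph all treat the comparison as agreement measured by the CCC, and the primary objective in 5.1 does not use the word. The two sections also fit together: 0.60 lies just below the substantial band and 0.81 is the cut for almost perfect, so rejecting H0 supports at least substantial agreement on the protocol's own scale. Section 11.1 adds a Bland-Altman analysis, which works on the scale of differences where equivalence would be judged. The mechanics of the test may sit in a statistical analysis plan that is not shown.

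Much of this stands. The plan is coherent as an agreement study, and the absence of test mechanics from 11.1 is not a fault in itself. But *equivalence* appears in both the synopsis and 9.1, the Bland-Altman graph has no limits to be judged against, and 0.60 is nowhere called a margin or justified as one. An analysis plan could add a confidence limit; it could not make a test of CCC above 0.60 support an equivalence endpoint. If only agreement was meant, correcting the word is the remedy.

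A reader might also infer that the study is mis-sized, or that the verbal bands are the rule for success. The documents support neither: the sample size reproduces, and 11.1 does not give the bands that role. A substantial label on an estimate and a non-significant test can both be true, so the secondary point is a risk of misreading, not a contradiction.

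**Conclusion.** The concern holds. The primary endpoint names a claim for which the protocol sets no criterion, and its only powered hypothesis can establish no more than a CCC above 0.60. With 50 patients that test is passed from an observed CCC of about 0.73, which supports at least substantial agreement on the protocol's scale but not equivalence. The unqualified bands in 11.1 are a lesser matter, uncommon in effect at the planned CCC and common only if the device falls moderately short of it.

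The conclusion about the claim needs only the protocol's wording. The figures rest on the one-tailed reading, the Fisher approximation and no systematic shift between devices; the limits of agreement also assume equal SDs.

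**What to change.** Before the data are analysed:

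1. In the synopsis and 9.1, replace equivalence with agreement, defined as a CCC above 0.60.
2. In 11.1, state the criterion already powered: the one-sided 95% lower confidence limit of the CCC exceeds 0.60 for one index that the sponsor names as primary. Treat the other indices and the Bland-Altman results as supportive.
3. Label the Landis-Koch bands as descriptive, and report the CCC with its confidence limit.
4. Keep equivalence only if the sponsor pre-specifies acceptable limits for the Bland-Altman differences and tests against them. The sample size would then have to be checked against those limits.

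Steps 1 to 3 cost some wording, one confidence limit and a less favourable claim. With a single primary index no extra patients are needed: power stays at about 91%, and an observed CCC of 0.81 would have a lower limit of about 0.71. If several indices must all pass, power is lower and the sample size should be reconsidered.

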11.3 Analysis set

Efficacy analyzes will be carried out on all patients who have completed the evaluation and whose data will be considered evaluable.

The following will be excluded from the statistical evaluation:

- all measurements lasting less than 4 ha cause the malfunction/
- malposition of the device
- data obtained from measurements of patients excluded from the study.

The safety analyzes will be carried out on all patients to whom the Soundi device and the polysomnography device (safety population) have been applied, regardless of the validity of the data collected.

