7.1 Compliance with procedures

All tests without artifacts invalidating the interpretation of one or more signals acquired for at least 4 hours of sleep will be considered valid.

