8.1 Interruption and withdrawal of subjects from the clinical investigation

Each patient is free to withdraw from the study at any time or his participation may be interrupted by decision of the trial for safety, behavioral or reasons administrative.

Reasons for discontinuing a patient's participation in the study may include:

- withdrawal of consent by the patient
- the change in the patient's clinical-functional conditions that do not allow participation
- lack of adherence to the procedures required by the study protocol on the part of the patient
- an adverse event (related or unrelated to the study device) which, in the opinion of the Principal Investigator, does not allow the continuation of the study itself.

If the study is interrupted for any of the reasons listed above, the measurements taken will not be considered in the statistical analysis.

The reasons for stopping the study will be recorded in CRF.

Unless particular problems are reported to the patient (adverse events or effects related to the use of the device in the study) which will be followed by specific assessments, a follow-up will not be necessary.

Patients excluded from the study and who cannot obtain the data required by the study protocol will be replaced to reach the required number.

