9.2 Secondary endpoint

The secondary endpoint of effectiveness of the clinical investigation is the evaluation of satisfaction with the use of SOUND I after the night of recording the parameters, through the patient's completion of a questionnaire prepared for the study.

10. Evaluation of the safety and vigilance of the medical device

The clinical investigation also aims to evaluate the safety and tolerability of the SOUNDI device by recording adverse events (secondary safety endpoint).

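### Satisfaction is classed as an effectiveness endpoint, so on a plain reading it is summarised only in patients with evaluable recordings, which probably biases it upward

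*Protocol*

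**What the plan says.** Section 9.2 of the protocol states: "The secondary endpoint of effectiveness of the clinical investigation is the evaluation of satisfaction with the use of SOUND I". Section 11.1, headed as the effectiveness analysis, gives the method: "Descriptive statistics will be used to evaluate the subject's satisfaction with using SOUNDI". Neither section names a population for the questionnaire.

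Section 11.3 sets two populations. For efficacy: "Efficacy analyzes will be carried out on all patients who have completed the evaluation and whose data will be considered evaluable". It also drops recordings shorter than 4 hours due to malfunction or malposition, and data from measurements of patients excluded from the study. For safety, everyone fitted with both devices counts, "regardless of the validity of the data collected". Section 11.4 adds that after bad positioning the patient's data stay out of the effectiveness analysis. Section 7.1 defines validity: "All tests without artifacts invalidating the interpretation of one or more signals acquired for at least 4 hours of sleep will be considered valid".

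Section 8.1 lists reasons for stopping. They include withdrawal of consent, non-adherence and "an adverse event (related or unrelated to the study device) which, in the opinion of the Principal Investigator" rules out continuing. It then says: "If the study is interrupted for any of the reasons listed above, the measurements taken will not be considered in the statistical analysis". Excluded patients who lack the required data "will be replaced to reach the required number". Section 13.6 makes any protocol deviation a ground for exclusion.

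Section 7 has the patient return both systems the next morning and fill in the questionnaire then.

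**The concern.** Evaluating patient satisfaction with SOUNDI is a stated secondary objective (section 5.2). Whether the signal can be scored has no bearing on whether a patient's opinion of wearing the device is valid. The efficacy set is nevertheless selected on the success of the recording and, through section 8.1, possibly on stopping for device-related reasons.

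Both can go with a poor experience. Section 3.3 names discomfort from the adhesive and allergic reaction to it as the main risks, and section 10.4 expects skin irritation. A patient whose unit failed or was badly placed, or who stopped because of such a reaction, wore the device and can answer the questionnaire. If these answers are left out and the patients replaced, the satisfaction summary describes a favourably selected group.

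**Working it through.** **Step 1: which population applies to the questionnaire.**

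| Link | Where | How firm |
|---|---|---|
| Satisfaction is an effectiveness endpoint | 9.2; placed under 11.1 | Stated |
| Effectiveness is analysed in completers with evaluable data | 11.3, and the synopsis | Stated |
| Bad positioning removes the patient's data from that analysis, not only the signal | 11.4 | Stated |
| Recordings under 4 hours from malfunction or malposition are dropped | 11.3 | Stated for recordings; reaches the questionnaire through the evaluable-data condition |
| Stopped patients are left out, including for a device-related adverse event or non-adherence | 8.1 | Depends on whether *measurements* covers the questionnaire |
| Excluded patients without the required data are replaced | 8.1 | Stated |
| The questionnaire is completed at device return | 7 | Stated; no valid signal is required |

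**Step 2: the plan's own figure.** The only related number is the sample size of 50 analysable patients (end of section 11.2), from a concordance correlation of 0.60 under the null and 0.81 under the alternative, 5% significance and 90% power. With the test read as one-sided and the Fisher z-transform:

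n = 3 + [(1.645 + 1.282) / (atanh 0.81 − atanh 0.60)]² = 48.5, so 49.

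Power at n = 50 is 90.8%. The stated 50 is reproduced, and nothing in this point changes it.

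**Step 3: formula for the bias.** Let f be the share of fitted patients excluded, S_E the proportion satisfied among evaluable patients, S_X the proportion among excluded patients, and D = S_E − S_X.

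- Reported figure: S_E
- All fitted patients: (1 − f)·S_E + f·S_X
- Bias: reported minus all fitted = f × D

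**Step 4: size.** The protocol gives neither f nor D, so every value here is an assumption. Bias in percentage points:

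| f | D = 0 | D = 30 | D = 50 | D = 70 |
|---|---|---|---|---|
| 5% | 0 | 1.5 | 2.5 | 3.5 |
| 10% | 0 | 3 | 5 | 7 |
| 20% | 0 | 6 | 10 | 14 |

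Two worked cases:

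- D = 50, with 80% of evaluable and 30% of excluded patients satisfied. At f = 10%, 0.9 × 0.80 + 0.1 × 0.30 = 75%. At f = 20%, 0.8 × 0.80 + 0.2 × 0.30 = 70%. The reported figure is 80% in both.
- D = 70, with 90% and 20% satisfied. At f = 10%, 0.9 × 0.90 + 0.1 × 0.20 = 83%. At f = 20%, 0.8 × 0.90 + 0.2 × 0.20 = 76%. The reported figure is 90% in both.

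**Step 5: how many patients.** With recruitment continuing to 50 evaluable patients, the number missing from the satisfaction result is 50/(1 − f) − 50: 2.6, 5.6 and 12.5 for f = 5%, 10% and 20%, or about 3, 6 and 13.

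**The case against.** The best defence is that the exclusion rules were written for recordings. Sections 8.1 and 11.3 speak of measurements, and a questionnaire is not naturally one. The evaluable-data condition could be applied endpoint by endpoint, so that for satisfaction it means a completed questionnaire. The effectiveness label is also thin: the synopsis lists satisfaction simply as a secondary endpoint beside safety, and the objectives group it with tolerability. This stands in part. It makes the reach of section 8.1 uncertain, but it does not remove the label in 9.2, the placement under 11.1 or the reference to patient data in 11.4.

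The population for a descriptive questionnaire summary is often left to the statistical analysis plan. Here, however, the protocol already supplies a rule, and a plan that follows it inherits the problem.

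Several stronger readings are tempting but not supported:

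- *That the rule removes the patients who tolerated SOUNDI worst.* This is an inference. Malfunction and malposition are technical or placement failures, and section 8.1 also lists changed clinical condition and unrelated adverse events.
- *That a patient who takes the device off during the night because of itching is certainly excluded.* The under-4-hour rule in 11.3 is tied to malfunction or malposition. On an assumed 10 p.m. start, removal at 2 a.m. would leave 4 hours, which could meet the threshold in 7.1. Stopping for an adverse event requires the Principal Investigator's judgement.
- *That every device fault loses a patient.* Section 11.4 allows the measurement to be repeated with another unit when a fault is signalled.
- *That the bias always favours the device.* That requires excluded patients to be less satisfied; with no gap the bias is zero.
- *That replacement conceals the loss.* Reasons for stopping go in the CRF, and the safety population keeps all fitted patients, with adverse events and device defects reported.

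**Conclusion.** The point holds in a limited form. On a plain reading of sections 9.2, 11.1, 11.3 and 11.4, satisfaction is summarised only in patients with evaluable recordings. For malfunction and malposition this follows from the text; for patients stopped under section 8.1 it is arguable. Because exclusion is plausibly related to dissatisfaction, an upward bias is likely, though not certain.

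Its size is 0 to 14 percentage points if 5% to 20% are excluded and the satisfaction gap is 0 to 70 points. Those ranges are assumptions. The endpoint is secondary and descriptive, and the reporting of adverse events in the safety population is not touched. The change is still worth making, because it removes a selection effect at almost no cost.

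**What to change.** - In sections 11.1 and 11.3, state that satisfaction is summarised in the existing safety population: all patients fitted with the devices who return a questionnaire, including those later replaced and whatever the validity of the recording. Report the number of missing questionnaires and the reasons.
- In sections 8.1, 11.3 and 11.4, limit the exclusions based on stopping, recording length and positioning to the agreement analysis.
- In section 8.1, state that patients who stop are asked for the questionnaire when they return the devices, unless they decline or withdraw consent.

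The cost is protocol wording and a few more questionnaires. The planned procedure already brings patients back with the devices, so no visit is added. The satisfaction figure may come out less favourable.

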11.4 Systematic errors - bias

Any distortions will be prevented by deriving the indices used for the diagnosis of respiratory and sleep disorders from both methods (Polysomnigraph and Soundi) using the same automatic analysis software (RemLogic).

This will then be followed by manual correction by the operator expert in sleep medicine who is blind to: the identity of the subject under examination, the device with which the data are obtained and the outcome of the same parameters obtained with the comparison device.

To document the patient selection bias, all reasons for non-participation in the study will be recorded on a specific form (Screening Log) and considered in the subsequent statistical analysis.

Impairment of the results or interpretation of the results may be caused by malposition or malfunction of the device.

Specifically, a check of all the sensors when the device is started was included in the design phase. In the event of a malfunction of one of them, it is signaled by a flashing red LED. In this case the measurement can be repeated with another device supplied.

In the event of bad positioning, the measurement results may be compromised and the signal may be incomparable with that acquired by the polysomnography machine. In this last case the measurement is unusable for the study and the patient data will not be included in the effectiveness analysis.

How to minimize these biases is further detailed in the dossier for the investigator.

12.Medical device

It is planned to use 2 experimental devices (SOUNDI system, Biocubica) and 1 product

comparison (polysomnograph, Embletta, Natus).

The experimental SOUNDI devices will be supplied by the Promoter and will be identified by a batch number and a serial number.

The Investigator will be responsible for keeping track of the experimental devices from their delivery to the center until they are returned to the Sponsor at the end of the study.

The devices will be stored centrally in a secure location where only authorized personnel can access them and at a temperature between -25°C and +70°C and a relative humidity of less than 93%, as indicated by the manufacturer, until delivery to the patient.

If a device is lost or damaged, the Investigator will notify it immediately to the Promoter.

The polysomnograph (Embletta, Natus) is already present at the center as it is used for clinical practice.

13. Ethical and regulatory aspects

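### Sections 7.1, 11.3 and 11.4 give no single evaluability rule for malpositioned but interpretable recordings of 4 hours or more, and excluding them under 11.4 can bias the primary CCC upward

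*Protocol*

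**What the plan says.** Three sections of the protocol bear on which paired recordings enter the effectiveness analysis.

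- **7.1 Compliance with procedures:** the validity rule is "All tests without artifacts invalidating the interpretation of one or more signals acquired for at least 4 hours of sleep will be considered valid". Neither cause nor device position is mentioned.
- **11.3 Analysis set:** the general condition is "Efficacy analyzes will be carried out on all patients who have completed the evaluation and whose data will be considered evaluable". What makes data evaluable is not defined there. The exclusion list follows: "all measurements lasting less than 4 ha cause the malfunction", then a slash, then "malposition of the device" on its own line, then data from patients excluded from the study.
- **11.4 Systematic errors - bias:** "In the event of bad positioning, the measurement results may be compromised and the signal may be incomparable with that acquired by the polysomnography machine". It continues: "In this last case the measurement is unusable for the study and the patient data will not be included in the effectiveness analysis". No duration limit is given.

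Two further statements matter. Section 8.1 says "Patients excluded from the study and who cannot obtain the data required by the study protocol will be replaced to reach the required number". The sample-size paragraph, printed under 11.2, says "A sample of 50 analyzable patients will guarantee a power of 90" per cent, for a CCC of 0.60 under the null against 0.81 under the alternative at a 5% level.

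**The concern.** The primary endpoint is agreement between SOUNDI and the polysomnograph, so recordings with large differences between the devices carry much of the information about failure. A malpositioned unit that still yields 4 or more interpretable hours is a likely source of such differences. The three sections do not settle whether that recording counts.

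The reason for removal matters as well. If a pair leaves the analysis because the SOUNDI signal does not compare with the reference, the exclusion depends on the quantity under study. Section 8.1 then allows the patient to be replaced, so the removal costs no sample size and leaves no gap in the count of 50. The reported CCC would describe recordings already screened for comparability. The blinding in 11.4 covers the manual correction of the signals. It does not clearly cover a judgement of comparability, which needs both signals.

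**Working it through.** **Step 1. The rules side by side**

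| Recording | 7.1 | 11.3 list, read as one joined item | 11.4 |
|---|---|---|---|
| Malpositioned, invalidating artifacts | not valid | listed only if under 4 h; may fail the evaluable condition | out |
| Malpositioned, interpretable, 4 h or more | valid | not listed | out, if bad positioning alone is enough; otherwise out if judged not comparable |
| Under 4 h because of malfunction or malposition | not valid | listed | out if malpositioned |
| Under 4 h for another reason | not valid | not listed | not addressed |

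The sections diverge in the second row. In the fourth row 7.1 and the 11.3 list differ, although other provisions may cover it (see the objection).

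**Step 2. The plan's own sample size**

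Inputs from the sample-size paragraph: CCC 0.60 under H0 and 0.81 under H1, 5% significance, 90% power. The garbled wording is read as a one-tailed z test.

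- Fisher z difference: atanh(0.81) − atanh(0.60) = 1.1270 − 0.6931 = 0.4339.
- ((1.645 + 1.282) / 0.4339)² = 45.5. Adding 2 or 3 gives n = 48 or 49, against 50 stated.
- Power at n = 50: Φ(0.4339 × √48 − 1.645) = 91.3%, or 90.8% with √47.

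The stated figure is reproduced.

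**Step 3. What keeping or dropping the recordings would do**

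Assumptions, none of them from the documents:

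- bivariate normal pairs with equal means and SDs;
- true CCC 0.81 in well-positioned recordings;
- m of 50 malpositioned recordings that pass 7.1 but have zero agreement with the polysomnograph.

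Under these assumptions the covariance shrinks in proportion, so the expected CCC with the recordings kept is about 0.81 × (50 − m)/50. Power comes from 20,000 simulated trials per scenario, using Lin's CCC with the Fisher z transform and a one-sided 5% test against 0.60.

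| m of 50 | 0.81 × (50 − m)/50 | Simulated median CCC, kept | Power, kept | Power, dropped and not replaced |
|---|---|---|---|---|
| 2 | 0.778 | 0.78 | 75% | 90% |
| 3 | 0.761 | 0.76 | 67% | 89% |
| 5 | 0.729 | 0.73 | 50% | 88% |
| 8 | 0.680 | 0.68 | 28% | 86% |

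With m = 0 the simulated power is 90.7%. The last column is lower than the protocol would produce. With replacement under 8.1 the analysed number returns to 50 and power to about 90%, while the CCC estimated is that of well-positioned recordings only.

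**The case against.** A reader might infer that 11.3 and 11.4 flatly contradict each other, with 11.3 keeping every full-night malpositioned recording and 11.4 dropping it. The text does not support that.

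- Section 11.3 never says its list is exhaustive, and it separately requires evaluable data. Exclusion rules can add up, and 11.4 can be read as naming one kind of non-evaluable recording.
- The 11.3 item is damaged. Taken exactly as printed, malposition is a separate bullet without a duration limit, and 11.3 then agrees with 11.4. The trailing slash makes the joined reading more natural, but it remains a reading.
- Section 11.4 is conditional. It can be read as removing only recordings whose signal turns out not to be comparable.
- A recording with invalidating artifacts already fails 7.1, so the conflict is confined to malpositioned recordings that remain interpretable.
- A short recording caused by the patient removing the unit may be covered by 8.1 (lack of adherence) or 13.6 (deviations as grounds for exclusion).
- The documents give no malposition rate, and zero agreement is close to the worst case.
- Whether to estimate agreement under correct placement or under all use is a legitimate design choice.

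These points limit the claim but do not remove it. The evaluable condition in 11.3 is undefined, and the nearest definition, 7.1, accepts the recording. If the bullets are literal, 7.1 still calls valid what 11.3 and 11.4 exclude. The narrower reading of 11.4 makes matters worse, because the exclusion then depends directly on agreement with the reference.

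**Conclusion.** The point holds as an unreconciled evaluability rule, with a route to upward bias in the primary CCC. It should be corrected before data are analysed.

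The finding rests on the text of 7.1, 11.3, 11.4 and 8.1. Its size rests on assumptions. With 2 to 5 of 50 interpretable malpositioned recordings at zero agreement, keeping them moves the median CCC from about 0.81 to 0.78–0.73 and power from about 90% to 75–50%. Fewer such recordings, or partial agreement in them, would give a smaller effect; with none, there is no effect.

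A reader might also infer that the sample size is wrong. It is not: 50 is stated as analysable patients, the figure reproduces, and excluded patients are replaced.

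**What to change.** State one rule and repeat or cross-refer to it in 7.1, 11.3 and 11.4:

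1. Recordings under 4 hours are not evaluable, whatever the cause. Delete the cause condition in 11.3.
2. Evaluability of longer recordings is decided by the 7.1 artifact and duration rule alone, without comparing the SOUNDI result with the polysomnograph result.
3. Report the CCC and Bland-Altman analyses both with and without malpositioned recordings of 4 hours or more that meet 7.1, giving the number of such recordings and the reason for each classification.
4. Name one of the two sets as primary in advance. The set that includes these recordings is preferable because it avoids selection on agreement. If the sponsor wants agreement under correct placement as the primary question, the protocol should say so and still show the other set.

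The cost is wording in three sections and one extra run of the same analysis, with no added procedures. If the inclusive set is primary and malposition occurs, the CCC and the power may be less favourable, by up to the amounts shown above under those assumptions.
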